14.4 Overall Survival

The overall survival (OS) time is defined as the date from first dose to death due to any cause:

OS = (date of event/censoring - date of the first dose + 1)/30.4375 (months).

For patients alive at the time of data cut-off date or who are lost to follow up, OS will be censored at the last date known to be alive.

The date of event / censoring is defined in Table.

Table 4 Survival Event / Censoring

	Date of event / censoring	Censoring
Participants alive or lost to follow-up before or at cut-off date	Last date known to be alive	Yes
Participants who died before or at cut-off date	Date of death	No

- All patient assessment dates (blood draws (laboratory, PK), vital signs, performance status, ECG, tumor assessments, quality of life assessments)
- Start and end dates of anti-cancer therapies administered after study treatment discontinuation.
- AE start and end dates
- Last known alive date in the "Survival Follow-Up" eCRF
- Study drug start and end dates
- Date of discontinuation from the "Study Termination" eCRF page (do not use if reason for discontinuation is lost to follow-up or death)

The last known to be alive date will be completed by the date of death for dead participants.

The analysis of OS will be performed with a Kaplan-Meier method (product-limit estimates) and a summary of associated statistics will be presented including corresponding two-sided 95% CIs. The CIs for the median will be calculated according to Brookmeyer and Crowley (1982) and CIs for the survival function estimates at Month 3, 6, and 12, 18, 24, 36, and 48 months (depending on actual data) will be derived using the log-log transformation according to Kalbfleisch and Prentice (1980) (CONFTYPE=loglog default option in SAS PROC LIFETEST). The estimate of standard error will be computed using Greenwood's formula. OS rates with their CI at 3, 6, 12, 18, 24, 36 and 48 months will be presented, as well as the number of participants at risk and failed.

A participant listing will provide the following information: dose level/cohort, participant identifier, age, sex, MSI status, PD-L1 expression, date of first administration, date of last tumor assessment, date of event/censoring, event/censoring reason, time to event.

14.5 **Subgroup Analysis**

BOR, DR, PFS according to RECIST 1.1 by Investigator and IRC, as well as OS analyses will be performed on subgroups as shown below:

Table 4 Efficacy assessments by subgroups

	BOR		PFS		DR ^a		os
	Inv	IRC	Inv	IRC	Inv	IRC	
BTC classification			✓	✓			✓
PD-L1 TC ^b	✓	✓	✓	✓	✓	✓	✓
PD-L1 TME ^b		✓		✓		✓	✓

PD-L1 WTU ^b		✓		✓	✓	✓
MSI		✓				
ADA	✓	✓	✓	✓		✓
nAb	✓	✓	✓	✓		✓

^a Only for dose expansion participants (excluding HCC)

ADA = antidrug antibody; BOR = best overall response; BTC = biliary tract cancer; DR = duration of response; HCC = hepatocellular carcinoma; Inv = Investigator; IRC = Independent Review Committee; MSI: Microsatellite Instability; nAb = neutralizing antibody; OS = overall survival; PD-L1 = programmed death ligand 1; PFS = progression-free survival.

Corresponding Kaplan-Meier figures will be provided for PFS, DR and OS. For BOR, corresponding spider plot will be displayed.

Patients with missing subgroup will not be included in analyses.

15 Anti-Drug Antibody and Neutralizing Antibody

15.1 Anti-Drug Antibody

Analysis Sets: Immunogenicity analysis set

Anti-drug antibody (ADA) will be assessed before the trial treatment start, and on Days 15, 29, 43, 57, 71, and 85 after the start of infusion, 6-weekly up to/including Week 25, every 12 weeks after Week 25, and during safety follow-up (the term HAHA is used in the eCRF). Samples collected after the on-treatment period (e.g. safety follow-up) will be included in the analysis as well. If the sample is positive for ADA, it will be re-analyzed to determine the titer. The ADA results will be derived based on the algorithm in Table 5.

Table 5 Algorithm for the Derivation of ADA Results

Sample Screen Result	Confirmatory	Titer	ADA Result
Negative	NA	NA	Negative
NR	NA	NA	NR
Positive	Negative	NA	Negative
Positive	NR	NA	NR
Positive	Positive	Number	Number
Positive	Positive	NR	Positive-TNR

NR = no result, NA = not applicable, TNR = titer no result.

Negative, number, or positive-TNR are valid results while number and positive-TNR are considered as positive. Participants will be characterized into different categories based on the criteria in

Table 6 below.

Table 6 Participants Characterized based on ADA Results

^b 1% cutoff

Category	Definition	Participant at Risk (Denominator for Incidence)
Never positive	No positive results at any time point	Number of participants with at least one valid result at any time point
Ever positive	At least one positive result at any time point, including baseline	Number of participants with at least one valid result at any time point
Pre-existing	A positive ADA result prior to treatment with bintrafusp alfa	Number of participants with valid baseline result
Treatment boosted	A positive ADA result prior to treatment with bintrafusp alfa and the titer ≥ 8*baseline titer at least one post-baseline value	Number of participants with valid baseline result and at least one valid post-baseline result
Treatment emergent	Not positive prior to treatment with bintrafusp alfa and with at least one positive post-baseline result	Number of participants with at least one valid post-baseline result and without positive baseline result (including NR)
Transient positive	If treatment emergent participants have (a single positive evaluation, or duration between first and last positive result <16 weeks) and last assessment not positive.".	Number of participants with at least one valid post-baseline result and without positive baseline result (including NR)
Persistent positive	If treatment emergent participants have duration between first and last positive result ≥16 weeks or a positive evaluation at the last assessment	Number of participants with at least one valid post-baseline result and without positive baseline result (including NR)

Start of ADA Immunogenicity Response (Seroconversion)

For participants with any positive ADA response, the date of the first assessment with positive ADA result will be considered as start date of ADA response.

Time to onset (weeks) of ADA response will be calculated as:

(Date of first positive ADA assessment – start date of bintrafusp alfa treatment + 1) / 7

Note: If the first positive is prior to the start of treatment, the formula is revised to:

(Date of first positive ADA assessment – start date of bintrafusp alfa treatment) / 7

Duration of ADA Immunogenicity Response

Duration of ADA immunogenicity response (weeks) is defined as:

(Date of last positive ADA assessment – date of first positive ADA assessment + 1) / 7

For participants with pre-existing positive, duration will be calculated from start date of bintrafusp alfa treatment rather than from date of first positive assessment. Participants still on treatment at the data cut-off and positive assessment at their last assessment before cut-off will be censored at the date of last assessment.

For ADA results, the following analysis will be described in each cohort and in all cohorts combined:

• The frequency and percentage of each ADA category will be tabulated

- The ADA titer value by timepoint will be summarized
- The maximum observed ADA titer per participant will be tabulated for each ADA status group. For each discrete titer value, percentages will be calculated using the total number of participants in each ADA status group as the denominator.
- The time to first ADA positive response will be summarized
- The duration of ADA immunogenicity response will be summarized

These analyses will be performed overall and by subgroups:

- Ethnicity (Japanese, Non-Japanese) for dose expansion participants (excluding HCC)
- BTC classification (Carcinoma of Vater's ampulla, Extrahepatic cholangio cell carcinoma, Gallbladder cancer, Intrahepatic cholangio cell carcinoma)

A listing of all individual ADA results from ever positive participants will be prepared by time point. The listing will include cohort, participant identifier, age, gender, race, ADA categories, date of assessment and results of screening, confirmatory and titer values.

A further listing will be provided including: cohort, participant identifier, age, sex, date of first ADA positive result, responder per IRC/investigator, date of response and timing of response related to the date of first ADA positive result. Responders will be defined as participants meeting confirmed CR or PR and non-responders as all other participants.

15.2 **Neutralizing Antibody**

Analysis Sets: Immunogenicity analysis set

Samples with a reportable ADA titer will also be tested in the two nAb assays, PD-L1 and TGFβ.

nAb results are positive or negative in a single assay and only derived when not performed because ADA was negative (see Error! Reference source not found. Table). Participants will be characterized in the two assays in different nAb categories based on the criteria in Error! Reference source not found.

Table.

 Table 7
 Algorithm for the Derivation of nAb Results

ADA Confirmatory Result	nAb Result	Derived nAb Result
Negative	NA	Negative
NR	NA	NR
NA (screen NR)	NA	NA
NA (screen negative)	NA	Negative
Positive	NR	NR
Positive	Positive	Positive

Positive Negative Negative

ADA = antidrug antibody, NA = not applicable, nAb = neutralizing antibody, NR = no result.

Table 8 Participants Characterized based on nAb Results

Category	Definition	Participant at Risk (Denominator for Incidence)
Never positive	No nAb positive results at any time point	Number of participants with at least one valid ADA result at any time point
Ever positive	At least one nAb positive result at any time point	Number of participants with at least one valid ADA result at any time point
Pre- existing	A positive nAb result prior to treatment with bintrafusp alfa	Number of participants with valid ADA baseline result
Treatment emergent	Not nAb positive prior to treatment with bintrafusp alfa and with at least one nAb positive post-baseline result	Number of participants with at least one ADA valid post-baseline result and without nAb positive baseline results (including missing, NR)
Transient positive	If treatment emergent participants have (a single nAb positive evaluation, or duration between first and last nAb positive result <16 weeks) and last ADA assessment not nAb positive.	Number of participants with at least one ADA valid post-baseline result and without nAb positive baseline results (including missing, NR)
Persistent positive	If treatment emergent participants have duration between first and last nAb positive result ≥16 weeks or a nAb positive evaluation at the last ADA assessment	Number of participants with at least one ADA valid post-baseline result and without nAb positive baseline results (including missing, NR)

ADA = antidrug antibody, nAb = neutralizing antibody, NR = no result.

Start of nAb Immunogenicity Response (Seroconversion)

For participants with any positive nAb response, the date of the first assessment with positive nAb result will be considered as start date of nAb response.

Time to onset (weeks) of nAb response will be calculated as:

(Date of first positive nAb assessment – start date of bintrafusp alfa treatment + 1) / 7

Note: If the first positive is prior to the start of treatment, the formula is revised to:

(Date of first positive nAb assessment – start date of bintrafusp alfa treatment) / 7

Duration of nAb Immunogenicity Response

Duration of nAb immunogenicity response (weeks) is defined as:

(Date of last positive nAb assessment – date of first positive nAb assessment + 1) / 7

For participants with pre-existing positive, duration will be calculated from start date of bintrafusp alfa treatment rather than from date of first positive assessment. Participants still on treatment at the data cut-off and positive assessment at their last assessment before cut-off will be censored at the date of last assessment.

For nAb results, the following analysis will be described in each cohort and in all cohorts combined:

- The frequency and percentage of each nAb category will be tabulated for each assay individually and combined.
- The nAb titer value by timepoint will be summarized
- The maximum observed nAb titer per participant will be tabulated for each nAb status group. For each discrete titer value, percentages will be calculated using the total number of participants in each nAb status group as the denominator.
- The time to first nAb positive response will be summarized
- The duration of nAb immunogenicity response will be summarized

These analyses will be performed overall and by subgroups:

- Ethnicity (Japanese, Non-Japanese) for dose expansion participants (excluding HCC)
- BTC classification (Carcinoma of Vater's ampulla, Extrahepatic cholangio cell carcinoma, Gallbladder cancer, Intrahepatic cholangio cell carcinoma)

Listings of nAb results from ever positive participants (in either assay) will be provided with the following: cohort, participant identifier, age, sex, race, assay (PD-L1 or $TGF\beta$), nAb categories status, visit, date of assessment and results of screening, and titer values.

A further listing will be provided including: cohort, participant identifier, age, sex, date of first nAb positive result, responder per IRC/investigator, date of response and timing of response related to the date of first nAb positive result. Responders will be defined as participants meeting confirmed CR or PR and non-responders as all other participants.

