7.7 Other Assessments

7.7.1 Anti-drug antibody Analysis

The blood sample for Baseline ADA analysis will be collected before trial treatment start. Further serum samples for ADA analysis will be collected as indicated in the Schedule of Assessments (Table 3). Whole blood (3.5 mL per sample) will be collected for ADA analysis at each sampling point.

57

Samples positive for ADAs will be re-analyzed to determine the titer.

The detection of antibodies to M7824 will be performed using a validated assay method with tiered testing of Screening, confirmatory, and titration. Confirmed positive antibodies may be tested for the presence of neutralizing antibodies and may be further characterized.

Further details will be summarized in the Laboratory Manual.

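### ADA and nAb duration comes out zero or negative when the only positive sample predates first dose, and the onset and duration summaries pool pre-existing with treatment-emergent positives

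*SAP*

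**What the plan says.** SAP 15.1 gives ADA duration in weeks as "Date of last positive ADA assessment – date of first positive ADA assessment + 1) / 7". For pre-existing positives it then moves the origin: "duration will be calculated from start date of bintrafusp alfa treatment rather than from date of first positive assessment". SAP 15.2 has the same structure for nAb, "Date of last positive nAb assessment – date of first positive nAb assessment + 1) / 7", and repeats the change of origin. Neither section sets a floor or an exclusion. SAP Tables 6 and 8 class a participant as pre-existing on a positive result before treatment alone; no later positive is needed.

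Onset is defined under a subheading on seroconversion. It covers everyone with a positive result: "For participants with any positive ADA response, the date of the first assessment with positive ADA result will be considered as start date". A pre-treatment first positive has its own rule, introduced by "Note: If the first positive is prior to the start of treatment, the formula is revised to", which drops the added day.

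The planned outputs include "The time to first ADA positive response will be summarized" and "The duration of ADA immunogenicity response will be summarized". They are given by cohort, for all cohorts combined, and by ethnicity and BTC classification. There is no split by pre-existing versus treatment-emergent status.

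On sampling, Protocol 7.7.1 states: "The blood sample for Baseline ADA analysis will be collected before trial treatment start". Protocol Table 3 marks that sample in the Screening column (Day -28 to first treatment), has no ADA mark at Day 1, and schedules the next sample at Day 15.

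**The concern.** Moving the origin to first dose changes the start of the interval but not its end. If the last positive sample is itself the baseline sample, the interval ends before it starts. The SAP anticipates a first positive before treatment when it defines onset, but has no matching provision for a last positive before treatment when it defines duration. The same paragraph also applies censoring to duration, and a negative time has no meaning there.

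The second issue is interpretation. An antibody present before the drug and one induced by it are different things, and a single pooled median describes neither. The SAP draws this line elsewhere: transient and persistent positivity apply only to treatment-emergent participants, and the trough concentrations by day relative to seroconversion (SAP 17.3) are restricted to them.

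Immunogenicity is a secondary objective (Protocol 4.2). SAP Section 4 names ADA duration and time to onset as new analyses for the CSR addendum and says the analyses may be used in regulatory submissions or manuscripts.

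**Working it through.** The plan states no numerical onset or duration, so there is no figure to reproduce. The check applies the SAP formulas to dates.

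**Notation.** Let d be days from first dose, with d = 0 on the dosing date, so that Treatment day = d + 1 from dosing onward.

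- Duration, pre-existing positive: (d_last + 1)/7
- Duration, all others: (d_last − d_first + 1)/7
- Onset: d_first/7 if d_first < 0, otherwise (d_first + 1)/7

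**Step 1: baseline sample is the only positive.** This covers participants whose later samples are all negative and those with no valid later sample.

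| Baseline sample, d | Duration (weeks) | Onset (weeks) |
|---|---|---|
| -28 | (-28+1)/7 = -3.86 | -4.00 |
| -21 | -2.86 | -3.00 |
| -14 | -1.86 | -2.00 |
| -7 | -0.86 | -1.00 |
| -2 | -0.14 | -0.29 |
| -1 | 0.00 | -0.14 |
| 0 | 0.14 | 0.14 |

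The general formula would give (d − d + 1)/7 = 0.14 in every row. The impossible values therefore come from the change of origin alone.

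**Step 2: at least one post-baseline positive.** With the last positive at Day 15, 29, 43 or 85, duration is 15/7 = 2.14, 29/7 = 4.14, 43/7 = 6.14 or 85/7 = 12.14 weeks. All are sensible values.

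**Step 3: pooling, onset (assumed data).** Take 10 ever-positive participants, k of them pre-existing and sampled 7 days before dosing (onset -1.00). The other 10 − k are the first entries of this invented list of first-positive days: 15, 29, 29, 43, 43, 57, 57, 71, 85, 85.

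| k | Median, treatment-emergent only (weeks) | Median, pooled (weeks) |
|---|---|---|
| 0 | 7.14 | 7.14 |
| 1 | 6.14 | 6.14 |
| 2 | 6.14 | 5.14 |
| 3 | 6.14 | 4.14 |
| 5 | 4.14 | 0.57 |

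A negative onset lies below every treatment-emergent onset. Pooling therefore lowers the mean and can never raise the median.

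**Step 4: pooling, duration (assumed data).** Take three treatment-emergent participants:

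- positive at Day 15 only: 1/7 = 0.14
- Day 29 to Day 57: (56 − 28 + 1)/7 = 4.14
- Day 29 to Day 85: (84 − 28 + 1)/7 = 8.14

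The median is 4.14 weeks. Adding two baseline-only positives sampled 7 days before dosing (-0.86 each) gives -0.86, -0.86, 0.14, 4.14, 8.14, with median 0.14. Adding instead two pre-existing positives last positive at Day 85 (12.14 each) gives 0.14, 4.14, 8.14, 12.14, 12.14, with median 8.14. The shift can go either way.

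**The case against.** The negative onset is deliberate. The SAP writes a rule for it, and dropping the added day fits SAP 9.3, which has no Treatment day 0. It correctly records that the antibody preceded the drug. This stands: the onset formula contains no arithmetic error.

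Other outputs keep the groups apart. Pre-existing and treatment-emergent are separate tabulated categories, and the listing of ever-positive participants shows ADA category, dates and results, so an odd value can be traced. Efficacy and safety are examined by ever versus never positive, not by onset or duration. SAP 9.10 plans no tests of study endpoints, and the protocol's secondary immunogenicity endpoint is titer (8.3.2). All this limits the consequences. It does not supply the missing duration rule or make the pooled medians readable.

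Three stronger readings are tempting, and the documents support none of them:

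- *Every pre-existing positive who turns negative on treatment gets an impossible duration.* Anyone still positive at Day 15 or later gets about 2 weeks or more, and a dosing-day baseline sample gives 0.14.
- *Both summaries are wrong.* This would need at least one pre-existing positive, and for an impossible duration at least one baseline-only positive. The documents give no counts.
- *Pooling makes induced antibody look shorter-lived.* Pre-existing positives who stay positive are counted from first dose, so they can lengthen the pooled duration.

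**Conclusion.** The point holds in a narrow form. The duration rule in SAP 15.1 and 15.2 returns 0 to -3.86 weeks for a participant whose only positive sample is a baseline sample taken 1 to 28 days before first dose. That follows from the stated formula and the screening window and needs no further assumption, apart from such a participant existing.

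The pooling issue is one of interpretation. Its size rests on the number of pre-existing positives, and for duration also on how long they stay positive. The effect ranges from none to material, and the figures in the illustrations are invented. Because these summaries are descriptive and no decision rule depends on them, this is a correction worth making rather than a threat to the trial's conclusions.

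**What to change.** In SAP 15.1 and 15.2:

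1. Summarize time to onset and duration for treatment-emergent participants, as Tables 6 and 8 define them.
2. Report pre-existing positives separately. Compute their duration from first dose only if at least one post-baseline sample is positive; otherwise report 'no post-baseline positive' with no duration.
3. Check addendum tables already produced for zero or negative durations and for pooled onsets before they are reused. SAP 6.1 records that the addendum was approved on 25 March 2021 and that no final analysis will follow, so any correction falls on existing output.

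The cost is SAP wording, a filter in two derivations for each of ADA and nAb, and the table check. The downside is a slightly smaller n in the main onset and duration tables.

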5.1.6 Planned Treatment Duration

The trial duration for a subject is estimated to be up to 2 years. This includes:

- Up to 28-day Screening period (decision will be made in this period for subjects' trial inclusion if all eligibility criteria are met).
- 21-day DLT evaluation period.
- 12-month treatment duration period until confirmed PD, unacceptable toxicity, or any criterion for withdrawal from the trial or IMP occurs (see Section 5.5).
- End-of-Treatment visit 28 days (± 5 days) after the last dose of MSB0011359C administration.
- Safety follow-up period 10 weeks (± 2 weeks) after the last administration of MSB0011359C.
- Long-term follow-up period: Subjects without PD at the End-of-Treatment visit will be followed up for disease progression (computed tomography [CT]/magnetic resonance imaging [MRI] scans every 12 weeks) until PD.
- Planned first subject in (dose escalation): First Quarter (Q1) 2016. Planned date last subject out (dose escalation): Q4 2020. Planned date last subject out (after expansion and follow-up): Q4 2020.

Subjects who have experienced a CR, PR or SD should continue treatment through the end of 12 months after confirmation, although additional treatment is possible. If the Investigator believes that a subject may benefit from treatment beyond 12 months, it may be permissible after discussion with the Medical Monitor. In the case of PD, subjects should continue treatment through their next tumor assessment, if they meet the criteria described in Section 5.5.1.

CONFIDENTIAL INFORMATION

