- Related TEAEs
- Related TEAEs by worst grade
- TEAEs leading to death
- Related TEAEs leading to death

Further TEAE tables will be presented by PT in descending order of frequency overall:

- TEAEs
- TEAEs, grade ≥ 3
- Related TEAEs
- Related TEAEs, grade ≥ 3
- Serious TEAEs
- Related serious TEAEs
- TEAEs leading to death

TEAEs and related TEAEs by worst grade will also be summarized, and the most frequent PT (at least 5%) will be presenting graphically by worst grade and PT with bar chart figures.

A listing of all adverse events (whether treatment-emergent or not) and a listing of TEAEs will be created separately with the relevant information.

Listing of adverse events will contain the following information: dose level/cohort, participant identifier, age, sex, preferred term, reported term for the adverse event, start date, end date, duration of AE (in days), day relative to the first infusion, day relative to the most recent infusion prior to AE onset, relationship to study treatment, toxicity grade, action(s) taken, outcome, TEAE (Y/N), seriousness (Y/N), AE before on-treatment period (Y/N), AE onset or worsening after on-treatment period (Y/N), AESI infusion-related (Y/N), medication administered. The listing will be sorted by dose level/cohort, participant identifier, and start date.

Evaluation of COVID-19 effects on AEs

The direct effect of COVID-19 for AEs will be assessed via listings of COVID-19 related AEs. The following listings will be generated using the 'COVID-19 related terms MedDRA 23.0 update Spreadsheet' (https://www.meddra.org/covid-19-related-terms-meddra-230-update-spreadsheet, last accessed on 28 May 2020) as available from Maintenance and Support Services Organization (MSSO), considering all 'search terms for COVID-19-related' ='Y'. The following information will be provided:

- Subject ID, country. age, sex, race
- Date of first, last treatment with study drug
- COVID-19-associated AE start date (day), COVID-19 associated AE stop date (day)
- AE preferred term, verbatim
- Toxicity grade
- Seriousness
- Relationship to treatment
- Action taken
- Outcome

The indirect effect of COVID-19 for AEs will not be assessed due to the low number of participants still on treatment at the onset of COVID-19.

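### ADA and nAb duration is censored only for participants still on treatment, so a participant who stopped while antibody-positive contributes a lower bound that is handled as complete

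*SAP*

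**What the plan says.** SAP 15.1 defines ADA duration in weeks as the span between the first and last positive results: "Date of last positive ADA assessment – date of first positive ADA assessment + 1) / 7". For participants positive before treatment, the span starts at the first dose. The one censoring rule is: "Participants still on treatment at the data cut-off and positive assessment at their last assessment before cut-off will be censored", at the date of that last assessment.

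SAP 15.2 repeats both for neutralizing antibodies: "Date of last positive nAb assessment – date of first positive nAb assessment + 1) / 7", with the same censoring sentence. Both sections say that duration will be summarized and name no method.

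Three other places bear on this:

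- SAP Table 6 classes a treatment-emergent participant as persistent positive on "duration between first and last positive result ≥16 weeks or a positive evaluation at the last assessment". Table 8 does the same for nAb. Neither asks whether treatment is continuing.
- Off-treatment samples count: "Samples collected after the on-treatment period (e.g. safety follow-up) will be included in the analysis as well". In the protocol schedule, the last ADA sample is at the safety follow-up visit: "Safety follow-up period 10 weeks (± 2 weeks) after the last administration of MSB0011359C". Table 3 and Section 7.1.5.2 show no ADA sampling in long-term follow-up.
- SAP 14.2 handles duration of tumor response differently. Participants without an event are right-censored at the last evaluable tumor assessment, with no on-treatment condition, and Kaplan-Meier is used.

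**The concern.** If the last available sample is positive, the end of the antibody response has not been seen. That is true whether or not the participant is still being dosed. Stopping treatment does not end positivity; it ends sampling some weeks later. Treatment status is therefore the wrong test for whether the end was observed.

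No rule covers a participant who stopped, died or left while positive. By the formula, that participant's duration runs to the last sample and carries no censoring flag.

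What is at stake is modest but real. Immunogenicity and its relationship to drug exposure is a secondary objective (Protocol 4.2). ADA duration is among the analyses that SAP Section 4 lists as new, and both ADA and nAb duration are also summarized by subgroup. SAP Section 4 allows these results to go into regulatory submissions or manuscripts.

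**Working it through.** The plan gives no duration figure, so there is none to reproduce. The check applies the SAP's formula and rule to example dates, asks how many participants the rule can reach, and then gives a hypothetical scale.

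**1. Same antibody history, different handling.** Suppose the first positive result and the last dose are both on Day 85, and the participant is still positive at safety follow-up 70 days later, on Day 155.

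- Duration = (155 − 85 + 1)/7 = 71/7 = 10.14 weeks. Off treatment, this is uncensored.
- The same two dates in a participant still on treatment also give 10.14 weeks, but censored.
- If treatment-emergent, both are persistent positive under Table 6.

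The number is the same in both cases, because the last assessment is itself the last positive. Only the censoring flag differs.

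**2. How many the rule can reach.**

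- Last participant started: 24 August 2017. Cut-off: 15 May 2020 (SAP Section 4). Difference: 995 days, and 995/30.4375 = 32.7 months.
- Planned treatment is 12 months, with extension possible (Protocol 5.1.6).
- SAP 16.1.1 drops an analysis "due to the low number of participants still on treatment at the onset of COVID-19". SAP 9.16 puts the start of that period no later than 11 March 2020, 65 days before the cut-off (20 + 30 + 15).
- Nobody started after August 2017, and SAP 9.15 reports no re-initiation. The number on treatment at the cut-off therefore cannot exceed the number at that onset.

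The on-treatment condition can hold for few participants. Most who were positive at their last sample will probably fall outside it.

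**3. Hypothetical scale.** Assume that true durations and the time to end of sampling are both exponential and independent. If a fraction p is positive at the last sample and none is censored, recorded duration is exponential with

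recorded mean (and median) = true value × (1 − p).

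| p | Recorded / true |
|---|---|
| 30% | 70% |
| 50% | 50% |
| 70% | 30% |

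**4. The same model with a Kaplan-Meier summary.** Let M be the true median, S the median time to end of sampling, and a the share still on treatment. Under the SAP rule the Kaplan-Meier median is 1/[1/M + (1 − a)/S]. For M = 26, S = 26 and a = 5%, this is 26/1.95 = 13.3 weeks. A simulation of 200,000 participants per setting gave:

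| True median (weeks) | Median end of sampling (weeks) | On treatment | Positive at last sample | SAP rule | Censor all positive at last sample |
|---|---|---|---|---|---|
| 26 | 16 | 5% | 62% | 10.2 | 26.0 |
| 26 | 16 | 20% | 62% | 11.3 | 26.0 |
| 26 | 26 | 5% | 50% | 13.3 | 25.9 |
| 26 | 26 | 20% | 50% | 14.5 | 26.0 |
| 52 | 16 | 5% | 76% | 12.8 | 52.0 |
| 52 | 16 | 20% | 77% | 14.5 | 52.3 |
| 52 | 26 | 5% | 67% | 18.0 | 52.3 |
| 52 | 26 | 20% | 67% | 20.0 | 52.2 |

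Every input in steps 3 and 4 is assumed. The model also ignores the visit grid, which widens to 6-weekly and then 12-weekly.

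**The case against.** The strongest reply is that the harm depends on a summary method the SAP does not name. As step 1 shows, the recorded value is the same with or without the flag. Under plain descriptive statistics, widening the censoring rule alone would change nothing. This stands, and it is why the fix must name the method as well. It does not rescue the plan: a plain summary would treat every lower bound as a final value, including those of the participants the SAP means to censor.

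It is also fair that the SAP never says in words that these durations are complete. That follows from the formula and the absence of any other rule. The individual dated ADA results of ever-positive participants are listed, so the information is not hidden.

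A reader might infer more than the documents support:

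- *That affected durations are short.* They are truncated at the last sample and may be long. Positive on Day 15 and still positive on Day 155 gives (155 − 15 + 1)/7 = 20.14 weeks.
- *That a single positive at the last sample, recorded as 1/7 = 0.14 weeks yet classed persistent, proves the rule contradicts itself.* That value comes from the formula and arises equally on treatment. Table 6 is a classification and the formula an observed span. The example shows the two treat unresolved positivity differently, no more.
- *That duration in this trial is understated by 30% to 70%.* The documents give no count of positives and no proportion positive at the last sample.

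On importance, the protocol's immunogenicity endpoint is serum titer (Protocol 8.3.2), not duration. No endpoint is tested (SAP 9.10), and the efficacy, safety and PK analyses by antibody status do not use duration.

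**Conclusion.** The point holds for both ADA and nAb. The stated rule makes censoring depend on treatment status when it should depend on whether the end of positivity was seen. The direction needs no distributional assumption: each affected value is a lower bound handled as complete, so duration is biased downward. Safety follow-up samples reduce the truncation but do not remove it.

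That the rule misses most participants positive at their last sample is probable rather than shown. It rests on the 995-day gap and the SAP's unquantified remark about those still on treatment. The size is unknown, and the percentages and medians under working are illustrations only.

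The consequence is confined to a secondary descriptive summary. It is worth correcting because the correction uses existing data.

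**What to change.** In SAP 15.1 and 15.2, replace the censoring sentence so that every participant whose last valid assessment is positive is censored at that assessment, regardless of treatment status. State that duration is summarized by Kaplan-Meier, with the number censored. Both parts are needed.

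The costs are:

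- The current SAP version is dated 11 April 2022, after approval of the CSR addendum on 25 March 2021, and no final analysis will follow. Duration outputs already reported in the addendum must be re-run or footnoted. No new data are required.
- Medians may not be estimable in small cohorts.
- Kaplan-Meier assumes that the end of sampling is unrelated to antibody persistence. Sampling stops soon after treatment does, often for progression or death, so the assumption should be stated beside the result.
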